## **14.4 Protocol Deviation Reporting**

Per the policy for Requirements for Source Documentation in DAIDS Funded and/or Sponsored Clinical Trials (available at the website referenced in [Section 11.2](#)), all protocol deviations must be documented in participant research records. Reasons for the deviations and corrective and preventive actions taken in response to the deviations should also be documented.

All DAIDS policies referenced in this section are available at:  
<https://www.niaid.nih.gov/research/daids-clinical-research-policies-standard-procedures>

Deviations should be reported to site IRBs/ECs and other applicable review bodies in accordance with the policies and procedures of these review bodies. Serious deviations that are associated with increased risk to one or more study participants and/or significant impacts on the integrity of study data must also be reported within IMPAACT, following procedures specified in the IMPAACT Manual of Procedures.

## **14.5 Critical Event Reporting**

Per the DAIDS policy on Identification and Classification of Critical Events, a critical event is defined as an unanticipated study-related incident that is likely to cause harm or increase the risk of harm to participants or others or has a significant adverse impact on study outcomes or integrity. All such events must be reported following procedures specified in the DAIDS Critical Events Manual, which is available at: <https://www.niaid.nih.gov/research/daids-clinical-research-event-reporting-safety-monitoring>

## **14.6 ClinicalTrials.gov**

This protocol is subject to the United States Food and Drug Administration Amendments Act of 2007 (FDAAA), including registration in ClinicalTrials.gov.

# **15 PUBLICATIONS**

All presentations and publications of data collected in this study are governed by NIH public access policy and IMPAACT policies, which are available in the IMPAACT Manual of Procedures.

171. De Sousa Mendes M, Hirt D, Urien S, Valade E, Bouazza N, Foissac F, et al. Physiologically-based pharmacokinetic modeling of renally excreted antiretroviral drugs in pregnant women. *Br J Clin Pharmacol*. 2015;80(5):1031-41.
173. Office of Behavioral and Social Sciences Research NIOH. Qualitative methods in health research: opportunities and considerations in application and review.
174. Patton MQ. Qualitative Research and Evaluation Methods. 3rd ed. Thousand Oaks, CA: Sage Publications 2002.
176. National Institutes of Health. Guidelines for the Inclusion of Women and Minorities as Subjects in Clinical Research. *Federal Register*; 1994 March 18.
177. National Institutes of Health. NIH Policy and Guidelines on the Inclusion of Children as Participants in Research Involving Human Subjects. 1998 March 6.

## Appendix IA (Schedules of Evaluation): Maternal PK Component Group 1 and Group 2

MATERNAL PROCEDURES	SCR	Entry (Day 0)	Week ( $\pm 1$ day)											Group 1 only
			1	2	3	4	5	6	7	8	9	10	11	
Informed Consent	X													
Medical and Drug History	X	X	X	X	X	X	X	X	X	X	X	X	X	X
Physical Examination	X	X				X				X				X
Study drug dispensing		X				X				X				
iNSC	X	X	X	X	X	X	X	X	X	X	X	X	X	X
Pregnancy Outcome														X
Demographic/Behavioral Questionnaires		X												X 
HIV RNA  ; store plasma for HIV drug resistance testing 	4mL	6mL				6mL				6mL				6mL
Rapid HIV 	X	X				X				X				X
TFV-DP level (DBS)		4mL	4 mL	4mL	4mL	4mL	4mL	4mL	4mL	4mL	4mL	4mL	4mL	4mL
Complete Blood Count	3mL													3mL
ALT, creatinine, CrCl	4mL					4mL								4mL
Hepatitis B surface antigen	3mL													3mL
Glucose (random)	1mL													
Chlamydia/gonorrhea (swab)		X												
Urinalysis (protein and glucose)	X													
Ultrasound (Group 1 only)	X													
Pregnancy Test (Group 2 only) 														X
Total maximum blood volume	15mL	10mL	4mL	4mL	4mL	14mL	4mL	4mL	4mL	10mL	4mL	4mL	4mL	21mL
														10mL

 If the participant has not delivered at 12 weeks of follow-up, participants may choose to continue in follow-up until delivery, refer to [Section 5.1.2.1](#)

 If within the window of one of the weekly visits, visits may be combined.

 Questionnaire is done at Week 12 visit only; questionnaire is not required at early D/C.

 If positive refer to [Section 6.3](#) and [Appendix IID](#) for additional procedures.

 Store plasma for HIV drug resistance testing at all visits indicated EXCEPT Screening.

 Blood collected for other tests will be used for the rapid HIV test. Collection of additional blood is not required.

 Urine (5mL) or blood (1mL) tests are acceptable. The total blood volume shown above accommodates collection of 1mL of blood, if needed.

## Appendix IB (Schedule of Evaluations): Infant PK Component Group 1

INFANT PROCEDURES: Group 1	Birth	PP Wk 6	Early D/C
Medical and Medications History	X	X	X
Physical Examination	X	X	X
Infant Feeding History	X	X	X
LABORATORY EVALUATIONS			
Creatinine	1mL	1mL	1mL
TFV-DP level (DBS)	0.5mL		
Total maximum blood volume	1.5mL	1mL	1mL

## Appendix IC (Schedule of Evaluations): Infant PK Component Group 2

INFANT PROCEDURES: Group 2	Entry (Day 0)	Wk 6	Wk 12 and Early D/C
Medical and Medications History	X	X	X
Physical Examination	X	X	X
Infant Feeding History	X	X	X
LABORATORY EVALUATIONS			
Creatinine	1mL	1mL	1mL
TFV-DP level (DBS)	0.5mL	0.5mL	
Total maximum blood volume	1.5mL	1.5mL	1mL

## Appendix IIA (Schedule of Evaluations): Maternal PrEP Comparison Component: Cohort 1, Cohort 2/Step 2

MATERNAL PROCEDURES:	SCR	Entry	Wk 4	Wk 8	Wk 12	Wk 24	Wk 36	L&D	PP Wk 6	PP Wk 14	PP Wk 26 / Exit and Early D/C	Interim Visit
Informed Consent	X											
Medical and Drug History	X	X	X	X	X	X	X	X	X	X	X	
Physical Examination	X	X	X	X	X	X	X	X	X	X	X	
Study drug dispensing		X	X	X	X	X	X	X	X	X		
Assess for social harms			X	X	X	X	X	X	X	X	X	
iNSC	X	X										X
iNSC with drug level feedback			X	X	X	X	X	X	X	X		
CASI evaluations and COVID-19 questionnaire		X	X	X	X	X	X			X	X 	
Qualitative IDI							X				X	
HIV RNA  ; store plasma for HIV drug resistance testing 	4mL	6mL	6mL	6mL	6mL	6mL	6mL	6mL	6mL	6mL	6mL	
Rapid HIV 	X	X	X	X	X	X	X	X	X	X	X	
TFV-DP level (DBS)		4mL	4mL	4mL	4mL	4mL	4mL	4mL	4mL	4mL	4mL	
Complete Blood Count	3mL										3mL	
ALT, creatinine, CrCl	4mL		4mL		4mL	4mL	4mL	4mL		4mL	4mL	
Hepatitis B surface antigen	3mL										3mL	
Syphilis		1mL									1mL	
HSV2		1mL									1mL	
Glucose (random)	1mL											
Chlamydia/gonorrhea (vaginal swab or urine)		X									X	
Microbiome (rectal swabs); if consent provided		X			X  (EGA 34-38/40 weeks)				X		X	
Microbiome (vaginal swab)		X			X  (EGA 34-38/40 weeks)				X		X	
Vaginal secretion sampling for drug level					X  (EGA 34 -38/40 weeks)				X		X	
Urinalysis (protein and glucose)	X											
Ultrasound	X											
DXA scan (Hip, Lumbar Spine) 								X			X	
Pregnancy Test 										X	X	
Total maximum blood volume	15mL	12mL	14 mL	10mL	14mL	14mL	14mL	14mL	10mL	18mL 	20mL 	

 CASI is done at Week 26 visit only; CASI is not required at early D/C.

 If positive refer to [Section 6.3.1](#) and [Appendix IID](#) for additional procedures.

 Store plasma for HIV drug resistance testing at all visits indicated EXCEPT Screening.

 Blood collected for other tests will be used for the rapid HIV test; collection of additional blood is not required.

 Collect sample at any visit which occurs at an estimated 34 – 38/40 weeks' gestation.

 DXA scan at Wk 26/Exit and early D/C (as applicable) must be preceded by a pregnancy test.

 Urine (5mL) or blood (1mL) tests are acceptable. The total blood volume shown above accommodates collection of 1mL of blood, if needed. Note: *Pregnancy testing may be done prior to the DXA scan at Wk 26/Exit and Early D/C and does not need to be repeated.*

As per [Section 6.5](#)

## Appendix IIB (Schedule of Evaluations): Maternal PrEP Comparison Component Cohort 2

MATERNAL PROCEDURES:	SCR	Entry	Wk 4	Wk 8	Wk 12	Wk 24	Wk 36	L&D	PP Wk 6	PP Wk 14	PP Wk 26 / Exit and Early D/C	Step Change	
												Visit 1	Visit 2
Informed Consent	X												
Medical and Drug History	X	X	X	X	X	X	X	X	X	X	X	X	X
Physical Examination	X	X	X	X	X	X	X	X	X	X	X	X	X
Study drug dispensing													X
Assess for social harms			X	X	X	X	X	X	X	X	X	X	X
iNSC	X	X	X	X	X	X	X	X	X	X	X	X	X
CASI evaluations and COVID-19 questionannire		X	X	X	X	X	X			X	X 	X	X
Qualitative IDI							X				X		
HIV RNA  ; store plasma for HIV drug resistance testing 	4mL	6mL	6mL	6mL	6mL	6mL	6mL	6mL	6mL	6mL	6mL	6mL	
Rapid HIV 	X	X	X	X	X	X	X	X	X	X	X		X
TFV-DP level (DBS)		4mL							4mL				4mL
Complete Blood Count	3mL										3mL		3mL
ALT, creatinine, and CrCl	4mL		4mL		4mL	4mL	4mL	4mL		4mL	4mL		4mL
Hepatitis B surface antigen	3mL										3mL		3mL
Syphilis		1mL										1mL	
HSV2		1mL										1mL	
Glucose (random)	1mL												1mL
Chlamydia/gonorrhea (vaginal swab or urine)		X										X	
Microbiome (rectal swabs); if consent provided		X	X  (EGA 34-38/40 weeks)						X		X		X
Microbiome (vaginal swab)		X	X  (EGA 34-38/40 weeks)						X		X		X
Urinalysis (protein and glucose)	X												X
Ultrasound	X												
DXA scan (Hip, Lumbar Spine) 									X			X	
Pregnancy Test 											X	X	
Total maximum blood volume	15mL	12mL	10mL	6mL	10mL	10mL	10mL	14mL	6mL	14mL 	16mL 	17mL	4mL

CASI is done at Week 26 visit only; CASI is not required at early D/C.

 If positive refer to [Section 6.3.1](#) and [Appendix IID](#) for additional procedures.

Store plasma for HIV drug resistance testing at all visits indicated EXCEPT Screening.

Blood collected for other tests will be used for the rapid HIV test; collection of additional blood is not required.

Collect sample at any visit which occurs at an estimated 34 – 38/40 weeks' gestation.

DXA scan at Wk 26/Exit and Early D/C (as applicable) must be preceded by a pregnancy test.

Urine (5mL) or blood (1mL) tests are acceptable. The total blood volume shown above accommodates collection of 1mL of blood, if needed. Note: *Pregnancy testing may be done prior to the DXA scan at Wk 26/and Early D/C and does not need to be repeated.*

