### **3.2.2 Exploratory Objective for PrEP Comparison Design**

The microbiome exploratory objective will assess whether PrEP alters the maternal and subsequently the infant microbiome. The samples for this objective will be collected during the regularly scheduled study visits - Entry, late pregnancy, and Weeks 6 and 26 postpartum - during the PrEP Comparison Component and will include maternal vaginal and optional rectal swabs. The Entry sample will serve as a baseline microbiome for the maternal participant during pregnancy. The re-sampling at 12 weeks will determine if the microbiome has changed significantly on FTC/TDF PrEP; pregnant women who decline PrEP will serve as the control group. The six-week postpartum time point will allow assessment of the microbiome composition after childbirth in women receiving or not receiving FTC/TDF PrEP. Finally, the 26-week postpartum time point will determine if the microbiome changes once pregnancy is over.

Infant rectal swabs or fresh stool will be collected at each timepoint to characterize the changes over time of the infant gut microbiome and potential changes resulting from exposure to maternal FTC/TDF PrEP. Changes in the microbiome will be assessed as described in [Section 9](#).

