## 6.2.1.2 PrEP Comparison Component Maternal Antepartum Week 4, 8, 12 (during pregnancy)

The Antepartum (AP) Week 4, 8 and 12 visits are targeted to take place on Study Days 28, 56 and 84 respectively, counted from the date of study entry as Day 0, with an allowable window of  $\pm 7$  days. A negative rapid HIV test result at each visit must be available, for participants in Cohort 1 and Cohort 2/Step 2, prior to prescribing study drug.

In addition to the standard of care HIV prevention package provided and routine safety evaluations for all study participants at these visits, adherence and acceptability assessments are performed in Cohort 1.

Participants in Cohort 1 and Cohort 2 may deliver prior to completion of the AP Week 8 or Week 12 visit. If so, evaluations indicated for the AP Week 8 and Week 12 visit should be conducted in addition to the evaluations required for the Maternal Labor and Delivery Visit (Week 0) ([Section 6.2.1.4](#)). In those cases, the visit window of the L&D visit (+14 days) will apply.

Note that women who are selected for and consent to participation in the Qualitative In-Depth Interview during pregnancy may be scheduled for their interview at or after the Week 12 visit. See [Section 6.2.1.8](#) for details about this visit.

PrEP Comparison Component Maternal AP Weeks 4, 8 and 12 ( $\pm 7$ days)		
Behavioral and Counseling		
 
CASI and COVID-19 questionnaire [see Section 6.16]
 
 
Week 12:
 
 
Qualitative IDI Visit [see Section 6.2.1.8]
 
 
Cohort 1 and Cohort 2/Step 2 only:
 
 
iNSC with drug level feedback [see Section 5.3.2]
 
 
Cohort 2 only:
 
 
iNSC [see Section 5.3.2]
 
Assess for social harms [see Section 13.6]
 

Clinical		
 
Obtain interim medical/medications history
 
Perform targeted physical exam
 
Identify/review/update adverse events
 
Perform additional evaluations per Section 8 and/or if clinically indicated (consult CMC if indicated)
 

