Laboratory	Blood	
Collect blood for:
 
 
HIV RNA test
 
Store plasma for HIV drug resistance testing
 
Rapid HIV test [see Section 6.3 in the event the test is (+)]
 
 
Weeks 4, 12:
 
 
ALT, Creatinine, and CrCl
 
 
Cohort 1 and Cohort 2/Step 2 only:
 
 
TFV-DP level (DBS)
 

	Other	
Collect vaginal swab once at EGA 34-38/40 weeks for:
 
 
Microbiome
 
 
Collect rectal swabs once at EGA 34-38/40 weeks (if consented) for:
 
 
Microbiome
 
 
Cohort 1 and Cohort 2/Step 2 only; collect at one visit at EGA 34-38/40 weeks:
 
 
Collect vaginal secretions for drug level
 

Study Drug		
Cohort 1 and Cohort 2/Step 2 only:
 
 
Prescribe and dispense study drug
 

### 6.2.1.3 PrEP Comparison Component Maternal Antepartum Week 24 and 36

Participants in both Cohort 1 and Cohort 2 who enroll early in gestation (i.e., prior to 20 weeks' gestation) may return for visits at AP Study Weeks 24 and 36. These visits are targeted to take place 168 and 252 days from the date of study entry (Day 0), respectively, with an allowable window of  $\pm$  14 days.

In addition to the standard of care HIV prevention package provided and routine safety evaluations for all study participants at these visits, assessments are conducted in the PrEP study cohort of PrEP acceptability and adherence.

Note that women who are selected for and consent to participation in the Qualitative In-Depth Interview during pregnancy may be scheduled for their interview at the time of their regular study visit at Week 24 or 36 or at an alternative date. See [Section 6.2.1.8](#) for details about this visit.

PrEP Comparison Component Maternal AP Week 24 and 36 Visit Procedures ( $\pm$ 14 days)	
Administrative and Regulatory	
 
Review locator information
 

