#### **Exploratory Objective 2.5.1:**

The distribution of maternal microbiome parameters in the PrEP and no PrEP groups will be described at the maternal (vaginal, gut) and infant (gut) sites. The changes in these parameters from entry to delivery will be evaluated according to PrEP use, and the relationship between vaginal microbiota and drug (PrEP) levels via univariate and multivariate regression models will be assessed. The potential effect of other factors, including recent antibiotic use, contraception use (including methods), and mode of delivery (i.e., vaginal vs. Caesarean delivery) will also be assessed.

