6.3 Primary Estimand(s) - PrEP Comparison Component

6.3.1 First Primary Estimand

Primary Objective 1: To characterize PrEP adherence among HIV-uninfected young women during pregnancy and for twenty-six weeks postpartum, when provided with enhanced adherence support through mobile technology and counseling based on observed drug levels.	
Estimand description	The probability that pregnant and postpartum HIV-uninfected women will have optimal adherence to daily oral PrEP 1) at defined timepoints; 2) during pregnancy and postpartum (through twenty-six weeks) as measured in TFV-DP concentration levels in dried blood spots during periods when women are formally prescribed PrEP

Treatment	
 1. Daily oral PrEP (200 mg FTC/ 300 mg TDF) during pregnancy and/or postpartum. 2. Enhanced adherence support, including SMS messaging and feedback of drug levels with tailored counseling. 3. Behavioral HIV risk reduction package
Target population	Analysis set
Women who are pregnant and HIV-uninfected, 16-24 years of age, with a confirmed singleton pregnancy of 32 weeks' gestation or less and who have access to a mobile phone, are able to receive and read SMS messages, and express willingness to take PrEP anytime between pregnancy and 26 weeks postpartum	Adherence set: Women initiating PrEP
Variable(s)	Outcome measure(s)
TFV-DP drug concentration level	
 1. TFV-DP drug concentration level from Dried Blood Spots (DBS) measured in pregnancy at 4, 8, 12, 24, 36 week study visits, Labor and Delivery, and postpartum at 6, 14, and 26 week study visits during the periods that participants are receiving PrEP. A binary indicator, "optimal adherence" will be defined as TFV-DP levels meeting or exceeding the threshold of consistent dosing of PrEP ("Green Zone") determined in the PK Component (Appendix Tables 1-2). For women who are pregnant the threshold is 600 fmol/punch if on PrEP \leq 6 weeks and 650 fmol/punch if $>$ 6 weeks; for women who are not pregnant the threshold is 700 fmol/punch if on PrEP \leq 6 weeks and 1050 fmol/punch if on PrEP $>$ 6 weeks. 2. Visits with optimal adherence according to TFV-DP level during pregnancy and during postpartum
Handling of intercurrent events	Handling of missing data

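### Antepartum visits are counted from study entry, so women enrolled at about 16–21 weeks have no visit at 34–38 weeks' gestation and their late-pregnancy swabs and vaginal drug level are missing by design

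*Protocol*

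**What the plan says.** For the first three antepartum visits, Protocol 6.2.1.2 says: "visits are targeted to take place on Study Days 28, 56 and 84 respectively". Day 0 is study entry, not a gestational age, and these visits may move by ±7 days. Section 6.2.1.3 adds that women enrolled before 20 weeks "may return for visits at AP Study Weeks 24 and 36". It fixes the dates as follows: "These visits are targeted to take place 168 and 252 days from the date of study entry (Day 0), respectively". These two may move by ±14 days. Protocol Appendix X and the SAP's analysis windows (SAP section 4) widen these to ±14 and ±21 days.

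The vaginal and optional rectal swabs (both cohorts) and the vaginal secretions for drug level (Cohort 1 and Cohort 2/Step 2) are due once in late pregnancy. Footnote 5 in Appendix IIA, repeated in Appendix IIB, gives the rule: "Collect sample at any visit which occurs at an estimated" 34–38/40 weeks. No visit is added to reach that interval.

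Three other texts describe the same sample or schedule:

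- Protocol 3.2.2 lists a late-pregnancy sample, as Table 7 does, but then says: "The re-sampling at 12 weeks will determine if the microbiome has changed significantly on FTC/TDF PrEP".
- Protocol 9.2.6, under objective 2.5.1, says: "The changes in these parameters from entry to delivery will be evaluated according to PrEP use".
- SAP 6.3.1 takes blood TFV-DP "measured in pregnancy at 4, 8, 12, 24, 36 week study visits", at Labor and Delivery, and postpartum.

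**The concern.** A sample due at a gestational age is attached to visits that run on a different clock. Whether a woman can give it depends on her gestation at enrollment. For a band of second-trimester entrants, no visit falls in the interval.

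This loss does not occur at random. Protocol 9.2.5 warns that the self-selected cohorts may differ in gestation at enrollment. If they do, the share without a late-pregnancy sample will differ by cohort as well. Among women who are sampled, time on PrEP at sampling also varies with entry gestation. The description of a 12-week re-sample is therefore true for only some of them.

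The same clock places the Week 24 visit at or after term for most women in this band, and the Week 36 visit after delivery for all of them. Yet the SAP lists both among the time points of a primary outcome.

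**Working it through.** **Inputs.** Visit weeks and windows come from Protocol 6.2.1.2, 6.2.1.3 and Appendix X. The sampling interval comes from Appendices IIA and IIB. Entry at 32 weeks or less, with no lower limit, comes from 4.2.1.2. Follow-up of 7–12 months comes from the Schema and 9.2.4. The half-life of 15.3 days in pregnancy comes from 1.3.3.1. Delivery at 40+0 weeks is my assumption (range 37–42).

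**Reproducing the plan's figures.** Weeks 4, 8, 12, 24 and 36 × 7 = 28, 56, 84, 168 and 252 days, as stated. Follow-up in weeks = (gestation at delivery − gestation at entry) + 26.
- Entry at 14, delivery at 40: 26 + 26 = 52 weeks, or 52 × 7 / 30.4375 = 12.0 months.
- Entry at 32, delivery at 37: 5 + 26 = 31 weeks, or 7.1 months.

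Both agree with the stated range.

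**Who has a visit at 34–38 weeks?** Gestation at visit = entry gestation g + study week. On target dates the interval is met if g is 30–32 (Week 4), 26–30 (Week 8), 22–26 (Week 12) or 10–14 (Week 24). With the protocol windows, Week 12 reaches 34 weeks when g + 13 ≥ 34, so g ≥ 21. Week 24 reaches 38 weeks when g + 22 ≤ 38, so g ≤ 16. Entry gestations with no possible visit, in weeks+days:

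| Windows used | Limit 38+0 | Limit 38+6 | Limit 40+0 |
|---|---|---|---|
| Target dates | 14+1 to 21+6 | 15+0 to 21+6 | 16+1 to 21+6 |
| Protocol (±7, ±14 days) | 16+1 to 20+6 | 17+0 to 20+6 | 18+1 to 20+6 |
| COVID-19 (±14, ±21 days) | 17+1 to 19+6 | 18+0 to 19+6 | 19+1 to 19+6 |

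The windows narrow the gap but never close it. Entry below 10 weeks (below 8 with protocol windows) is a second gap, but those women fall outside the expected follow-up: entry at 8 with delivery at 40 gives 58 weeks, or 13.3 months.

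**Weeks 24 and 36.** For entry at 14, 16, 18 and 20, Week 24 falls at 38, 40, 42 and 44 weeks' gestation. For entry at 14–22, Week 36 falls at 50–58 weeks. It precedes a 40-week delivery only for entry before about 4 weeks (6 with the window). Set against the stated follow-up, the earliest Week 36 visit under protocol windows is at Week 34, and 34 + 26 = 60 weeks, or 13.8 months. Taking the earliest COVID-19 day at both ends, 33 + 23 = 56 weeks, or 12.9 months. Both exceed 12.

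**Time on PrEP at the late-pregnancy sample.** On target dates it is 4, 8, 12 or 24 weeks, depending on g. It is 12 weeks only for entry at 22–26.

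**Blood TFV-DP for entry at 16–20.** Week 12 falls at 28–32 weeks' gestation, 56–84 days (8–12 weeks) before a 40-week delivery. The Labor and Delivery waiver in 6.2.1.4 applies only if the last visit was within 30 days, so the blood spot is due. Even for delivery at 37 weeks the interval is at least (37 − 32) × 7 = 35 days. Of the drug present at Week 12, 2^−(56/15.3) = 8% remains after 56 days, so the delivery level is driven by dosing after Week 12. A sample 14 days after birth still carries 2^−(14/15.3) = 53% of the level at delivery.

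**The case against.** The strongest reply is that this is a modest loss on an exploratory objective. That largely stands. The swabs and vaginal drug level serve objective 2.5.1, which the Primary SAP leaves to a separate plan. Sites can use the windows to sample women enrolled at 14–16 or 21–22 weeks. The Week 24 and 36 visits are optional in wording. With no lower gestational limit, a rarely used column is not in itself an error.

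The footnote's wording could also be stretched to an unscheduled visit. But the Interim Visit column of Appendix IIA lists counseling only, and Protocol 6.5 lets that visit take place by telephone.

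Three stronger readings are tempting, and the documents do not support them:

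- A reader might infer that the pregnancy adherence estimate describes only the first 12 weeks on drug. The Labor and Delivery blood spot is required, is a listed SAP time point, and reflects late-pregnancy dosing.
- A reader might put a percentage on the women affected. An even spread of entry over 14–32 weeks would give 44% on target dates, 28% with protocol windows and 17% with COVID-19 windows (33%, 17% and 6% with a 40-week limit). That spread is an assumption, and the figure ranges from 6% to 44%. The PK Component's median entry of 18 weeks came from a group restricted to 14–24 weeks and does not transfer.
- A reader might infer that a PrEP effect cannot be separated from gestation. Cohort 2 is sampled under the same rule and is the stated control group, so the cohorts can be compared at equal gestation.

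Replacing Weeks 24 and 36 outright would also do harm. A woman enrolled at 8 weeks now has a visit at 32 weeks. She would instead go from 20 to 34–38 weeks without one.

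**Conclusion.** The concern holds for the late-pregnancy vaginal and rectal swabs and the vaginal drug level. On target dates, women enrolled at 14+1 to 21+6 weeks have no visit at 34–38 weeks. At 16+1 to 20+6 weeks, no date within the protocol windows can supply one, and at 17+1 to 19+6 weeks none within the COVID-19 windows can. The band is narrower if the limit is 40 weeks. These results assume the woman is still pregnant at the visit; earlier delivery can only widen the gap. The share of women affected cannot be computed from the documents.

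The primary adherence outcome is preserved. On target dates, women entering at 16–20 weeks lack a scheduled blood spot for about 8–12 weeks between Week 12 and a 40-week delivery, and no more than that.

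Three inconsistencies stand without any assumption about entry gestation. The analysis of change to delivery has no maternal microbiome sample at delivery. The same sample is called both late-pregnancy and 12-week. Week 36 is an adherence time point that the stated expected follow-up leaves no room for.

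**What to change.** 1. In Protocol 6.2.1.3 and Appendices IIA and IIB, keep the Week 24 visit for very early entrants. Where it would fall after 38 weeks' gestation, bring that planned visit forward to 34–38 weeks, with its listed procedures.
2. Amend footnote 5 so that a woman with no scheduled visit expected at 34–38 weeks gives the sample at Week 12. This covers entry at 20 to just under 22 weeks, for which no Week 24 visit is planned and Week 12 falls at 32 to just under 34 weeks. Record gestation and weeks on PrEP at sampling, and include both in the objective 2.5.1 model. State whether the upper limit is 38 or 40 weeks.
3. In Protocol 9.2.6, define the change as entry to the late-pregnancy sample, and reconcile 3.2.2 and Table 7 with it.
4. In SAP 6.3.1, remove Week 36 as an adherence time point or justify it.

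The cost is a protocol amendment, plus one antepartum visit actually attended by women for whom it now falls after term. With a visit at 34–38 weeks, the 30-day waiver at Labor and Delivery will apply more often, so the amendment should say whether the delivery blood spot remains due.
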